# 1. Glossary

Cl Chief Investigator

DAH30 Days alive and at home at 30 days

eCRF Electronic Case Report Form

EOT End Of Trial

GCP Good Clinical Practice

HRA Health Research Authority

INH Volatile-based Inhalational Anaesthesia
IRAS Integrated Research Application System

ISF Investigator Site File

Participant An individual who takes part in a clinical study

PI Principal Investigator

QMUL Queen Mary University of London

REC Research Ethics Committee

TIVA Total Intravenous Anaesthesia

TMF Trial Master File

# 3. Summary and Synopsis

Short title	GlucoVITAL				
Methodology	National, multi-centre randomised trial				
Objectives	
 
Measuring intraoperative glucose levels
 
Examine whether total intravenous anaesthesia (TIVA) reduces postoperative complications (myocardial injury and/or infections) by limiting hyperglycaemia after major noncardiac surgery
 
Detecting the individual's risk of developing injurious perioperative hyperglycaemia
 
				
Number of participants	450 participants				
Eligibility criteria	Patients aged 50 years and over undergoing elective major noncardiac surgery under general anaesthesia				
Statistical methodology and analysis	For the primary outcome of intraoperative blood glucose				
Study duration	36 months				

#### 4. Introduction

# 4.1. Background

The frequent development of high blood glucose levels (stress hyperglycaemia) early during major surgery is consistently and dose-dependently associated with myocardial injury and infections, both of which prolong hospitalisation and accelerate mortality even after discharge from hospital. The majority of individuals who experience complications after surgery associated with hyperglycaemia do not have diabetes mellitus. Hyperglycaemia, which occurs in part through the development of insulin resistance, exacerbates systemic inflammation through acute oxidative stress, leading to organ injury. The risk of sustaining myocardial injury and infections doubles with hyperglycaemia, yet routine detection of injurious levels of hyperglycaemia is not a routine feature of current practice. Moreover, anaesthetic techniques that limit stress hyperglycaemia are unexplored, despite substantial mechanistic differences between intravenous and inhalational anaesthetic agents that alter the risk of disrupting normal glucose control.

The surgical backlog presents a huge challenge to not only increase surgical throughput, but also ensure complications after noncardiac surgery are minimised. At least 50% of individuals develop high blood glucose levels (hyperglycaemia) after tissue injury/trauma 8, which are associated with, and mechanistically linked to, organ injury and infections after surgery. Numerous mechanisms are likely to contribute to perioperative hyperglycaemia, characterized by a state of insulin resistance - a state of decreased biological response to insulin. Many individuals without diabetes mellitus have established insulin resistance before surgery, a key component of metabolic syndrome which is present in ~25% of the UK population. Mitochondrial bioenergetics controls insulin sensitivity by regulating the cellular redox environment, with impaired mitochondrial electron transport and fatty acid oxidation evident in insulin resistance across diverse tissues. Acquired mitochondrial and glycolytic dysfunction occurs in circulating lymphocytes after surgery, as quantified by ex- vivo respirometry, leading to impaired functionality and cell death. Acute loss of adaptive immune cells results in the failure to temper the inflammatory response generated by the initial innate response to tissue injury. Reduced numbers of Tcells exacerbate systemic inflammation 14, 15 and increases the risk of infection 16 and organ injury, including after surgery.

Despite these startling links and potentially treatable perioperative abnormalities, routine detection of perioperative hyperglycaemia is not a routine feature of current practice in individuals without diabetes mellitus, unless they are admitted to a high-dependency/critical care unit.

Paradoxically, poor outcomes have been repeatedly shown to occur in patients without diabetes who develop perioperative hyperglycaemia, compared with patients with diabetes mellitus. Rational therapy is limited by the lack of easy-to deliver glucose monitoring at scale,1 as well as ongoing controversy over limiting serious side effects of hypoglycaemia frequently associated with exogenous insulin therapy. Postoperative hyperglycaemia may be the most important risk factor for surgical site infections. A Cochrane analysis found insufficient evidence to support strict glycaemic control versus conventional management (maintenance of glucose <10mmol.L-1) for the prevention of surgical site infections. These data are limited by methodological quality, including small sample sizes in single-centre studies plus inconsistencies in glucose measurement and outcome measures. Perioperative hyperglycaemia is also associated with excess myocardial injury. Sustaining subclinical myocardial injury is associated with higher risk of mortality one year after surgery.

Recently, another key study has reported outcomes in 4899 non-diabetic individuals in whom a very high prevalence of blood glucose testing (75%) occurred within 24 hours after surgery. Hyperglycaemia was defined, a priori, as blood glucose level of ≥7.8mmol/L within 24 hours after surgery. This study confirmed that patients without diabetes mellitus had worse outcomes than patients with diabetes at similar levels of hyperglycaemia. The authors speculated insulin may mitigate this effect, but this has huge implications for service delivery, patient safety and would require a complete redesign of perioperative glucose monitoring to identify patients who may benefit from treating higher glucose levels. However, the challenges of insulin administration at scale, plus the frequent danger of hypoglycaemia as illustrated by the NICE-SUGAR trial in critically ill patients, suggests that alternative therapies to minimise blood glucose require exploration. Ideally, a real-time monitor to alert clinicians to injurious levels of hyperglycaemia in a non-critical care setting and/or a preoperative test to detect individuals most at risk would rationalise resources. That is now a reality – albeit untested- using continuous (interstitial) glucose monitoring.

#### 4.2. Rationale

Our aims of the study are to provide detailed data describing the below questions:

- 1. Measuring intraoperative glucose levels.
- 2. Examine whether total intravenous anaesthesia (TIVA) reduces postoperative complications (myocardial injury and/or infections) by limiting hyperglycaemia after major noncardiac surgery.
- 3. Detecting the individual's risk of developing injurious perioperative hyperglycaemia.

#### 4.3. Risks / Benefits

This trial poses no additional risks as we are comparing two modes of anaesthesia that are part of usual care. Blood samples will be obtained at convenient times to minimise patient inconvenience.

# 5. Study Objectives

#### 5.1. Primary objective

To identify association between intraoperative glucose levels and the mode of anaesthesia (TIVA vs inhalational) in patients undergoing major noncardiac surgery.

# 5.2. Secondary objectives

- Measure days alive and at home at 30 days (DAH30)
- Establish the interaction between absolute glucose levels and mode of anaesthesia in the perioperative period
- Measure hyperglycaemia profiles in relation to myocardial injury
- Measure hyperglycaemia profiles in relation to postoperative infection
- Can patients with, or susceptible to insulin resistance be identified prior to surgery

# 5.3. Primary clinical outcome measure

The primary outcome is blood glucose measurements via:

 Blood-Gas measurements for glucose before surgery, the end of surgery and on day one after surgery.

# 5.4. Secondary clinical outcome measures

- DAH30 is a continuous number between 0 and 30, reflecting the total number
  of days that a patient spends alive and at home within 30 days after surgery.
  In this definition, home reflects any place other than hospital. If a patient dies
  within those 30 days, their value is set to 0. DAH30 captures the development
  of all-cause complications which prevents patients leaving hospital after
  surgery.
- Increase in serum high sensitivity troponin-T (Elecsys, Roche Diagnostics)
   concentration of:
  - a. An absolute value of ≥15ng L on day one after surgery
     OR
  - b. An increase of  $\geq 5$  ng L from the preoperative value on day one after surgery when the preoperative value of  $\geq 15$ ng L
- Incidence of postoperative infection within 30 days after surgery. This is defined as one or more of the following infections of Clavien-Dindo grade II or greater. A full list of definitions is available in Appendix A:
  - a. Superficial surgical site infection;
  - b. Deep surgical site infection;
  - c. Organ space surgical site infection;
  - d. Pneumonia;
  - e. Urinary tract infection;
  - f. Laboratory confirmed blood stream infection;
  - g. Infection, source uncertain; this is defined as an infection which could be more than one of the above (i.e. a-f), but it is unclear which.
- Continuous glucose measurements using continuous glucose monitoring (CGM) up to 10 days after surgery or hospital discharge whichever is sooner.

# 5.5. Secondary mechanistic laboratory outcome measures

- Plasma C-peptide measurements before surgery and on day one after surgery.
- Insulin measurements before surgery and day one after surgery.

- Flow cytometry assessment of metabolic dependence of leukocytes before surgery, the end of surgery, day one after surgery and on day of hospital discharge.\*
  - \* This will only be done at selected sites.

# 6. Study Design

#### 6.1. Study setting

National, multi-centre randomised trial.

#### 6.2. Inclusion criteria

- Aged ≥ 50 years
- Elective major noncardiac surgery under general anaesthesia (as per PQIP inclusion criteria)
- Written informed consent for trial participation

#### 6.3. Exclusion criteria

- Known contraindication to either TIVA or inhalational anaesthesia
- Clinical refusal
- Procedures where the participant is not expected to survive for 30 days
- Previous participating and completion in the GlucoVITAL trial
- Patient unable to give informed consent or complete questionnaires

# 7. Study Procedures

#### 7.1. Participant identification

During the trial recruitment period, hospital research teams will liaise with clinical staff to identify individuals with upcoming major noncardiac surgery that may be eligible for enrolment. Based on this referral, a member of the team delivering the trial at the hospital (e.g. clinician, nurse or research practitioner) with appropriate knowledge will formally assess eligibility of the participant against trial inclusion and exclusion criteria. No additional tests or investigations will be required for assessing eligibility.

#### 7.2. Informed consent considerations

Potential participants will be screened by research staff at the site having been identified from pre-admission clinic lists, operating theatre lists and by communication with the relevant nursing and medical staff. Before surgery, potential participants will be identified and approached by a member of the research team, who are considered part of the direct care team. This may be conducted via telephone, post, online or face-to-face consultations and provides an opportunity for the research team to explain the trial to the participants in detail. Patient information sheets can be posted or emailed to participants for their perusal and consideration. The participant will be approached prior to surgery at the first suitable opportunity to allow time for any questions. It is recommended (although not mandated) that the participant is approached at least one day prior to the date of surgery. Written informed consent must be obtained before surgery and can be obtained using either paper or electronic systems depending on individual sites arrangements. It is the responsibility of the Principal Investigator (PI) at each site, or persons delegated by the PI to obtain written informed consent from each potential participant prior to participation in this trial. This process will include provision of a patient information sheet accompanied by the relevant consent form, either paper or electronic, and an explanation of the aims, methods, anticipated benefits and potential hazards of the trial. The PI or designee will explain to all potential participants that they are free to refuse to enter the trial or to withdraw at any time during the trial, for any reason. If new safety information results in significant changes in the risk/benefit assessment, the patient information sheet and consent form will be reviewed and updated if necessary. The PI or designee will assess potential participant's capacity to give informed consent, and those who lack capacity to give or withhold informed consent will not be recruited. If a participant loses capacity during their participation in the trial, the original consent by the participant will be respected. If this situation occurs, clinical outcome data will continue to be collected, but participant questionnaires will not need to be completed. Patients who are not entered into this trial should be recorded (including reason not entered) on the electronic patient-screening log provided to sites in the Investigator Site File.

#### 7.3. Randomisation

Participants will be randomised on a 1:1 basis to receive either TIVA or inhalational anaesthesia by a computer generated procedure. This computerised procedure will use a minimisation algorithm to ensure balance in treatment arm allocation across the following four stratification variables, factors thought to affect outcome either

through treatment effectiveness or underlying prognosis, also permitting appropriate exploratory subgroup analyses:

- 1) Surgical speciality (musculoskeletal/intra-abdominal/thoracic/vascular/other)
- 2) Expected duration of surgery (<2hours, ≥2hours)
- 3) Cancer surgery/non-cancer surgery
- 4) Preoperative frailty (Rockwood Frailty Score) Well/Vulnerable/Frail

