# 7.4. Randomising on the day of surgery

Recruiting centres will be asked to randomise participants on the day of surgery, once the planned surgery is confirmed as taking place. There will be occasions when surgery is cancelled at the last minute and rescheduled to another day. If the participant is happy to remain in the trial, recruiting centres will be asked to inform the GlucoVITAL team of the new surgery date as soon as possible, and data collection timepoints will be adjusted. Participants should receive their original allocated intervention at their new scheduled surgery date. If the surgery is cancelled indefinitely, or the participant is no longer suitable for the trial, the recruiting centre will be asked to inform the GlucoVITAL team as soon as possible.

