#### 7.5. Trial intervention

Anaesthesia will be administered by experienced anaesthetists and delivered according to local guidelines. All other participant care will be conducted as per routine clinical practice. More detailed information regarding trial intervention will be provided to sites as part of the trial-specific training.

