#### 7.5.1. Total Intravenous Anaesthesia (TIVA)

Participants randomised to the TIVA arm of the trial will have their maintenance of anaesthesia performed with intravenous anaesthetic agents as determined by the treating anaesthetist. Administration of TIVA will not be protocolised and will be left to clinical discretion for management. Maintenance of general anaesthesia should be via TIVA only. During training, it will be emphasised that clinicians should not expose TIVA group participants to inhaled anaesthetic agents.

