#### 7.5.2. Volatile-based Inhalational Anaesthesia (INH)

Participants randomised to the INH arm of the trial will have their maintenance of anaesthesia performed with inhalational volatile-based anaesthetic agents as

determined by the treating anaesthetist. Administration of INH will not be protocolised and will be left to clinical discretion for management. Maintenance of general anaesthesia should be via inhalational route only. During training, it will be emphasised that clinicians should not expose INH group participants to intravenous anaesthetic agents.

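### Recruiting centre is in neither the minimisation (Protocol 7.3) nor the stated arm comparisons (section 10): no bias, but a small, recoverable loss of precision

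*Protocol*

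**What the plan says.** The trial is described in section 6.1 as a "National, multi-centre randomised trial". Under 7.3, "Participants will be randomised on a 1:1 basis to receive either TIVA or inhalational anaesthesia", using a "minimisation algorithm to ensure balance in treatment arm allocation across the following four stratification variables". The list is closed, and nothing elsewhere says that allocation is balanced by centre. Under 7.4, "Recruiting centres will be asked to randomise participants on the day of surgery".

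Much of what surrounds the outcome is local:

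- Section 7.5: "Anaesthesia will be administered by experienced anaesthetists and delivered according to local guidelines", with all other care following routine practice.
- Section 7.5.1: "Administration of TIVA will not be protocolised and will be left to clinical discretion for management". Section 7.5.2 says the same of the inhalational arm: "Administration of INH will not be protocolised and will be left to clinical discretion for management".
- Section 7.7: infection is assessed first by a site research associate, and a positive call is then confirmed or refuted by the site principal investigator, with no central adjudication.
- Section 5.5, on flow cytometry: "This will only be done at selected sites".

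For analysis, section 10 names a two-sample t-test or a rank-sum test for blood glucose and a chi-squared test for myocardial injury and/or infection. It mentions repeated-measures analyses as further comparisons. No centre term appears in any of these.

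**The concern.** Section 7.3 gives its reason for choosing the four factors: they are believed to influence outcome, through treatment effectiveness or through prognosis. By that criterion centre is an obvious candidate here, since the interventions are not protocolised and one component of the composite is judged on site.

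Balance on the four factors across the whole trial does not balance the arms within a centre, or within the group of sites doing flow cytometry. If centres differ in glucose rise or infection rate, an unadjusted comparison carries those differences as noise. What is at stake is precision, and how readily a reader can see that site differences do not drive the result.

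**Working it through.** **Inputs from section 10.1.** Difference 0.6 mmol/L, SD 1.8 mmol/L, two-sided 5%, power 90%, 2% dropout, N = 390. Flow cytometry: difference 4%, SD 7%, 2% dropout, N = 133. Composite: 56% versus 40%, 4% dropout, N = 450. The planned total is 450 (section 3).

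**Assumed, because the protocol gives no value.** Centre ICC for glucose change 0.02 to 0.10; 10 or 20 centres of unequal size; minimisation with a 0.8 biased coin.

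**Step 1: reproduce the stated sizes.**
- Primary: 2 × (1.960 + 1.282)² × (1.8/0.6)² = 189.1, so 190 per arm, or 191 on the t distribution. 382/0.98 = 389.8, giving 390.
- Flow cytometry: 2 × (1.960 + 1.282)² × (7/4)² = 64.4, so 65 per arm. 130/0.98 = 132.7, giving 133.
- Composite, with continuity correction: 216 per arm. 432/0.96 = 450.

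All three agree with the protocol.

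**Step 2: what removing centre variance is worth.** Suppose the SD of 1.8 includes between-centre variation. With arms balanced within centres and centre in the model, the residual SD is 1.8 × √(1 − ICC). Power is then Φ(0.6 / [1.8 × √(1 − ICC) × √(2/191)] − 1.960). At ICC 0 this is Φ(0.6/0.1842 − 1.960) = Φ(1.297) = 90.3%. The equivalent sample size is 390 × (1 − ICC).

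| ICC (assumed) | Power, 382 analysed | Equivalent to N = 390 | Power, 441 analysed (450 × 0.98) |
|---|---|---|---|
| 0 | 90.3% | 390 | 93.8% |
| 0.02 | 90.8% | 382 | 94.2% |
| 0.05 | 91.7% | 370.5 | 94.9% |
| 0.10 | 93.0% | 351 | 95.8% |

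The gain is 0.5 to 2.7 points at 382 analysed, and 0.4 to 2.0 points at the planned enrolment.

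**Step 3: simulation of the allocation** (N = 382, 1000 runs per scenario, assumptions as above).
- Four-factor minimisation, unadjusted test: the mean estimate is about 0.60 for a true 0.6. Type I error is 3.6% to 6.6% (Monte Carlo standard error about 0.7 points, so compatible with 5%). Power is 89.7% to 91.2%.
- Same allocation, adjusted for centre: power 88.0% to 92.4%.
- Centre added to the minimisation and adjusted for: power 89.7% to 93.5%.
- Mean within-centre arm difference falls from about 4.3 to 1.7 patients (10 centres), or from about 3.1 to 1.6 (20 centres), when centre is a minimisation factor.

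The Monte Carlo standard error of a power near 90% is √(0.9 × 0.1/1000) = 0.9 points, so the simulated power ranges are not sharply separated. A further simulation with a random intercept (10 or 20 centres, N = 382) showed essentially no cost at ICC 0 and a gain of about 0.5 to 2.5 points at ICC 0.02 to 0.10.

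**Step 4: flow-cytometry subset.** If 130 analysed patients split 53/77 instead of 65/65, power falls from 90.3% to about 89.3%, one point.

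**The case against.** The strongest reply is that this is a design choice, not an error. Section 7.3 justifies its factors, and leaving centre out has a rationale. Sites randomise locally and the anaesthetist must know the allocation, so balancing within small centres makes the next assignment easier to guess. That stands, and it is why the change to the algorithm is only optional here.

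A reader might infer more than the documents support:

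- **That local practice is confounded with treatment, or that false positives are inflated.** It is not. Allocation is individual and 1:1, so each centre's practice applies to both arms. Imbalance at a small centre is ordinary sampling error, and the simulated estimate is unbiased with type I error near 5%.
- **That different blood-gas analysers distort the primary result.** The protocol does not say where the analyser is. Section 10 defines the outcome as a change, so a constant offset cancels within a patient measured on one machine. Troponin goes to a central laboratory, C-peptide and insulin go to one laboratory, and the sponsor supplies the continuous monitor.
- **That the flow-cytometry subset is at serious risk.** A range of ±23 for the arm difference among 133 patients (1.96 × √133) assumes simple randomisation and ignores the minimisation. Simulating four-factor minimisation, with assumed factor prevalences and a subset drawn at random, gives about ±19. The power cost is about one point for an exploratory outcome.

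It can also be said that covariates belong in the statistical analysis plan, which is not shown and may add centre. That carries some weight. But section 10 does not leave the method open: it names unadjusted tests, and a later plan would have to depart from them. Nor could a later plan restore balance in the allocation itself.

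**Conclusion.** The point holds as a minor weakness. Neither the allocation nor the stated analysis accounts for centre, in a multi-centre trial where care is local and infection is decided on site. The consequence is chance imbalance within centres, plus whatever between-centre variance exists left in the error term.

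For the primary outcome that is worth roughly 0.5 to 3 power points. The size rests wholly on the assumed ICC of 0.02 to 0.10; with an ICC near zero there is nothing to recover. Planned enrolment of 450 against a requirement of 390 already gives more cover than this loss. No gain has been calculated for the chi-squared comparisons. The case for acting is that the remedy needs no extra patients or data.

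**What to change.** **Analysis (recommended).** In section 10, replace the unadjusted comparisons with models containing treatment arm, the four minimisation factors and a random intercept for recruiting centre. Use a linear mixed model for glucose change and the continuous mechanistic outcomes, including the flow-cytometry subset. Use a logistic equivalent for myocardial injury and/or infection, reported also as a standardised risk difference so that the result stays on the scale of the sample-size calculation. State a fallback in case the centre variance cannot be estimated, which is most likely in the flow-cytometry subset if few sites take part. Report arm counts by centre and within the flow-cytometry sites.

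The cost is a few lines of protocol text and one added model term, made before unblinded data are seen. Centre is already known for every participant.

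**Allocation (optional).** If the randomisation system can still be changed, add centre as a fifth minimisation factor and state a random element. This is a configuration change. Its downside is slightly more predictable allocation at small open-label sites, which the random element limits but does not remove. If recruitment is too advanced, the analysis change alone is enough.
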